16.6. Appendix 6: Derived and Transformed Data

16.6.1. General

Multiple Measurements at One Analysis Time Point

- Where multiple assessments are made, the mean of replicate assessments at any given time point will be used as the value for that time point. This derived mean will be reported in the listing in addition to the individual assessments.
- If there are two values within a time window the value closest to the target day for that window will be used (with the exception of the worst case summaries for parameters detailed in Section 16.3 for SRT outputs, where the worst case would be used). If values are the same distance from the target, then the mean will be taken.
- Participants having both High and Low values for Normal Ranges at any post-baseline visit for safety parameters will be counted in both the High and Low categories of "Any visit post-baseline" row of related summary tables. This will also be applicable to relevant Potential Clinical Importance summary tables.

Study Day

- Calculated as the number of days from randomisation date:
 - Ref Date = Missing → Study Day = Missing
 - Ref Date < Randomisation Date → Study Day = Ref Date Randomisation Date
- Ref Date ≥ Randomisation Date → Study Day = Ref Date (Randomisation Date) + 1

Actual Relative Time

- Calculated as the time in days or fraction of a day before or after first dose
 - This will be calculated relative to exposure date and time for both pre- and post- dose assessments where relevant.
 - This provides an alternative to 'Study Day' with a meaningful value of 0 and is of benefit for profile plots showing results before and after dosing.

16.6.2. Study Population

Treatment Compliance

Total number of doses received and number of doses withheld are summarised for treatment compliance.

Number of doses withheld will be calculated only for subjects who attended the study visit and dose was withheld, but will not include the subjects who missed dosing visits.

Exposure

Duration of exposure for the treatment phase will be calculated based upon the following formula. If a subject has at least 28 days of information after their last dose:

Duration of exposure in days = treatment stop date - treatment start date + 29

If a subject withdraws from the study or dies with less than 28 days of information after their last dose:

Duration of exposure in days = Date of withdrawal or death - treatment start date +1

201247

This assumes patients are exposed for a 28-day period post-dosing, in-line with the half-life of GSK2330811.

Demographics

Age

- Only birth year is captured on the eCRF, therefore GSK standard IDSL algorithms will be used for calculating age where birth date will be imputed as follows:
 - The missing date and month will be imputed as '30th June'.
- Birth date will be presented in listings as 'YYYY'.

Body Mass Index (BMI)

• Calculated as Weight (kg) /Height (m)2

Disease Specific

Time from onset of the first non-Raynaud's phenomenon manifestation and Raynaud's phenomenon manifestation

Time in months calculated as date of first screening visit from onset of the first non-Raynaud's phenomenon manifestation.

Partial dates will be imputed as follows:

- o Any subject with a missing day will have this imputed as day '01'.
- Any subject with a missing date and month will have this imputed as '1st January'.

Time in months will be rounded up to the nearest whole month for each subject before being summarised.

Baseline Autoantibody

Numeric results of RNA Polymerase III Antibody - Standard will be classified as,

Positive, if numeric values ≥20 and Negative, if numeric values <20.

DLCO

During study set-up, the Respiratory Function eCRF screen was set up to collect the screening DLCO (uncorrected for Hb) and DLCO (corrected for Hb) values in mL/min/mmHg. However, part way through the study, the team became aware that these results were being reported locally in different units (in some cases different than the units required per the eCRF), and some sites did not convert the values to the required eCRF units. A note to file in the eTMF documents the corrective and preventative actions. DLCO summary tables will present data using ML/MIN/MMHG and therefore data collected using unit MMOL/MIN/KPA will be transformed using the following formula:

ML/MIN/MMHG =MMOL/MIN/KPA x 2.987.

Based on information from data management (documented in the note to file) sites collected DLCO using the following units:

Site id	Unit
PPD	ML/MIN/MMHG
	MMOL/MIN/KPA
	MMOL/MIN/KPA
	MMOL/MIN/KPA
	MMOL/MIN/KPA

201247

PPD	MMOL/MIN/KPA	
	MMOL/MIN/KPA	
	ML/MIN/MMHG	
	ML/MIN/MMHG	

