5.4. Scientific Rationale for Study Design

As this is the first study of GSK2330811 in participants with SSc, and the first repeat dose study, the primary endpoint is the safety and tolerability of GSK2330811. In addition, this study will include assessments of the pharmacokinetics, target engagement and downstream pharmacology of GSK2330811. This will be achieved by assessing GSK2330811 and OSM levels in blood and skin blister fluid and mRNA markers of GSK2330811 pharmacology in skin biopsies. Skin involvement is emphasised because it is readily studied, contributes substantially to the morbidity experienced by patients with dcSSc and exemplifies the three major pathological processes involved in the condition.

The assessment of biomarkers of fibrosis, inflammation and vasculopathy in blood and skin biopsies will also be performed, and for this reason the population is enriched for early active disease. Changes in these parameters and their association with each other and with preliminary measures of clinical efficacy will be assessed. These data are intended to provide evidence that GSK2330811 is having an impact on key pathways involved in the pathogenesis of SSc.

The purpose of cohort 1 is to evaluate the safety and tolerability of repeat doses of a pharmacologically active but submaximal dose of GSK2330811, before escalating to a higher dose.

The 12 week duration of the Treatment Phase is based on the expectation that an effective therapy should cause changes in the mechanistic parameters at this timepoint [Guo, 2015; Khanna, 2016; Rice, 2015].

The GSK2330811 half life is between 19 to 25 days, consistent with a typical monoclonal antibody half life for a soluble cytokine (see IB for GSK2330811) [GlaxoSmithKline Document Number 2016N284919_00]. Participants will be followed for approximately 18 weeks after the last administration of GSK2330811.

The placebo group is required for a valid evaluation of adverse events attributable to GSK2330811 treatment versus those independent of GSK2330811 treatment. The placebo participants will also serve as negative controls for the biomarker and efficacy assessments.

Participants will be randomised in a 3:1 ratio to GSK2330811 and placebo respectively. This unbalanced allocation ratio means that more participants are available for the assessment of within-participant changes in biomarkers after dosing with GSK2330811 and allows more participants to receive GSK2330811.

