5.5. Dose Justification

Dose levels for this study have been selected on the basis of PK/PD predictions, data from the first time in human study with GSK2330811 and preclinical data. Two dose levels (a 100 mg sub-maximal dose to test initial safety and tolerability and a 300 mg maximal dose to test POM) have been selected based on predicted target engagement after repeat dosing.

An in-vivo affinity of approximately 0.6 nM was estimated from first time in human data. The typical GSK2330811 apparent distribution volume was 11.5 L (95% Confidence Interval (CI): 10.2-13.1) and the typical apparent systemic clearance was 14.1 mL/hr (95% CI: 12.7-15.6). The mean terminal half-life ranged between 19 and 25 days. The ratio of GSK2330811 mean concentration between skin blister fluid and plasma ranged from 19 to 45%.

A target-mediated drug disposition (TMDD) model (Mager, 2005) using a one-compartment PK model together with binding kinetics of drug and target was developed to predict target engagement after repeat dosing.

First cohort: 100 mg every other week is considered a sub-maximal pharmacologically active dose with a predicted target engagement of approximately 80% in serum at trough.

Second cohort: 300 mg is predicted to achieve engagement of greater than 90% of OSM in serum at trough.

In addition a PKPD model was developed to assess the relationship between drug concentration and platelet count reduction [Wang, 2010] including a feedback mechanism. According to the model predictions after repeat dosing at 100 mg every other week, no participant is anticipated to achieve a CTCAE grade 2 or greater reduction in platelet count.

The NOAEL in the 13 weeks cynomolgus monkey study was 300 mg/kg/week. The PK exposure achieved in cynomologous monkey was more than 100 times greater than the predicted PK exposure in human (steady state AUC 21300ug.h/mL and Cmax 68.2ug/mL) at a dose of 300 mg every other week [GlaxoSmithKline Document Number 2016N284919_00].

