16.4. Appendix 4: Study Phases and Treatment Emergent Adverse Events

16.4.1. Study Phases

In general, assessments and events will be classified according to the time of occurrence relative to study treatment start date. Specific rules for Concomitant Medications and Adverse Events are specified in the section below.

Treatment Phase	Definition
Pre-Treatment	Date < Study Treatment Start
On-Treatment	Study Treatment Start ≤ Date ≤ Study Treatment Stop Date +28 days
Follow up	Study Treatment Stop Date +28 days < Date

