16.12.5. Safety Tables

Safety: Tables						
No.	Population	IDSL / TST ID / Example Shell	Title	Programming Notes	Deliverable	
Adverse	e Events					
3.1.	Safety	AE1	Summary of All Adverse Events by System Organ Class and Preferred Term, by Treatment Phase	For IA1, don't present by phase and remove ', by Treatment Phase' from the title. Add a row to include number of participants contributing to treatment phase and use as denominator. Add footnote 'Note: On treatment phase defined as period from first dose to last dose + 28 days. Follow up phase defined as period after last dose + 28 days.'	IA1, IA2, Adhoc DRC, SAC	
3.2.	Safety	AE3	Summary of Common (>=5%) Adverse Events, by Treatment Phase	Add a row to include number of participants contributing to treatment phase and use as denominator. Add footnote 'Note: On treatment phase defined as period from first dose to last dose + 28 days. Follow up phase defined as period after last dose + 28 days.'	SAC	
3.3.	Safety	AE15	Summary of Common (>=5%) Non-serious Adverse Events by System Organ Class and Preferred Term (Number of Subjects and Occurrences)		SAC	
3.4.	Safety	AE5A	Summary of Adverse Events by System Organ Class and Preferred Term and Maximum Intensity, by Treatment Phase	Add a row to include number of participants contributing to treatment	SAC	

Safety:	Safety: Tables						
No.	Population	IDSL / TST ID / Example Shell	Title	Programming Notes	Deliverable		
3.5.	Safety	AE1	Summary of Drug-Related Adverse Events, by Treatment Phase	phase and use as denominator. Add footnote 'Note: On treatment phase	SAC		
3.6.	Safety	AE5A	Summary of Drug-Related Adverse Events by System Organ Class and Preferred Term and Maximum Intensity, by Treatment Phase	defined as period from first dose to last dose + 28 days. Follow up phase defined as period after last dose + 28 days.'	SAC		
3.7.	Safety	AE3	Summary of Non-Serious Drug-Related Adverse Events, by Treatment Phase		SAC		
Serious	AEs	I					
3.8.	Safety	AE1	Summary of Non-Fatal Serious Adverse Events, by System Organ Class, by Treatment Phase	Add a row to include number of participants contributing to treatment phase and use as denominator. Add footnote 'Note: On treatment phase defined as period from first dose to last dose + 28 days. Follow up phase defined as period after last dose + 28 days.'	SAC		

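### The SAP's 28-day post-dose cut is only 1.1 to 1.5 half-lives, and at the final analysis the main adverse event tables are split there with no whole-period participant count listed

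*SAP*

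**What the plan says.** SAP 16.4.1 (Study Phases) defines on-treatment as "Study Treatment Start ≤ Date ≤ Study Treatment Stop Date +28 days"; anything later is classed as follow-up. The footnotes to the adverse event tables in SAP 16.12.5 repeat this: "On treatment phase defined as period from first dose to last dose + 28 days".

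SAP 16.6.2 (Study Population, Exposure) uses the same end point for participants with at least 28 days of information after the last dose: "Duration of exposure in days = treatment stop date - treatment start date + 29". Its justification is "This assumes patients are exposed for a 28-day period post-dosing, in-line with the half-life of GSK2330811".

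Protocol 5.4 states "The GSK2330811 half life is between 19 to 25 days", and Protocol 5.5 agrees: "The mean terminal half-life ranged between 19 and 25 days". Protocol 5.4 also follows participants for about 18 weeks after the last dose.

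The leading adverse event display, Table 3.1, is titled "Summary of All Adverse Events by System Organ Class and Preferred Term, by Treatment Phase". Its programming note uses the number of participants contributing to each phase as the denominator. Tables 3.2, 3.4 to 3.9 and 3.11 to 3.14 follow the same pattern. Tables 3.3 (common non-serious events) and 3.10 (serious events) are not split.

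**The concern.** A half-life is the time taken to lose half of the drug. It does not mark the end of exposure. If the cut falls while concentrations are still in a pharmacologically active range, events arising under substantial exposure are reported in the follow-up columns, and the stated duration of exposure stops while drug is still present.

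Adverse event reporting is the first primary endpoint in both documents, and safety is assessed descriptively without testing, so the layout of these tables carries the result. A reader who wants the number of participants with any event after first dose cannot add the two phases, for two reasons: a participant with events in both would be counted twice, and the denominators differ. Cohort 2 has a planned minimum of about 20 participants at 3:1, so about 15 are on active drug. One participant moved between columns changes an on-treatment proportion by about 1/15 = 6.7 percentage points.

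**Working it through.** **Inputs.** From Protocol 5.5: CL/F 14.1 mL/h (95% CI 12.7 to 15.6), V/F 11.5 L (10.2 to 13.1), half-life 19 to 25 days, a one-compartment kinetic model, and predicted steady-state AUC 21,300 ug.h/mL and Cmax 68.2 ug/mL at 300 mg every other week. From Protocol 5.1: six doses 14 days apart, the last on Day 71. The absorption rate ka is not given, so it is an assumption and is varied below.

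**Reproducing the protocol's figures.**
- AUC at steady state = dose/(CL/F) = 300/0.0141 = 21,277 ug.h/mL, against 21,300 stated.
- Half-life = ln 2 × 11,500/14.1 = 565 h = 23.6 days, inside 19 to 25.
- The stated Cmax of 68.2 lies between the steady-state average (21,277/336 h = 63.3) and the instant-absorption limit (77.3). A ka of 0.375 per day matches it.

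**Where the cut falls.**
- Study day: 71 + 28 = Day 99. Exposure for a full course: 71 − 1 + 29 = 99 days.
- In half-lives: 28/25 = 1.12 to 28/19 = 1.47.
- Fraction remaining by simple decay: 2^(−28/19) = 0.36 to 2^(−28/25) = 0.46.

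**300 mg at the cut against the 100 mg on-treatment peak.** With instant absorption and six doses in each group, the ratio is 3 × 2^(−28/t), where t is the half-life in days. Instant absorption gives the smallest ratio of the absorption rates tried.

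| Half-life (days) | Absorption | 300 mg, 28 days after dose 6 (ug/mL) | 100 mg peak (ug/mL) | Ratio |
|---|---|---|---|---|
| 19 | instant | 22.4 | 20.7 | 1.08 |
| 23.6 | instant | 31.0 | 23.6 | 1.32 |
| 23.6 | ka 0.375/day | 33.7 | 20.7 | 1.63 |
| 25 | ka 0.1/day | 43.7 | 19.9 | 2.20 |

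- Over half-lives of 19 to 25 days, with instant absorption or ka of 0.1 to 1.0 per day, the ratio runs from 1.08 to 2.20.
- At the two extreme corners of the CL/F and V/F confidence intervals (fastest and slowest elimination) it runs from 1.07 to 2.33.
- With instant absorption it reaches 1 at day 28 only if the half-life is 28/log2(3) = 17.7 days, below the protocol's range.
- At the typical half-life the 300 mg level falls below the 100 mg peak at about 37 days (instant absorption) to 45 days (ka 0.375/day) after the last dose. At 19 days with instant absorption it does so at about day 30.

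The comparison matters because the protocol regards the lower dose as active: "100 mg every other week is considered a sub-maximal pharmacologically active dose with a predicted target engagement of approximately 80% in serum at trough".

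**Reporting consequence.** For the final analysis (SAC in the SAP), the listed tables compare as follows.

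| Content | Table split at 28 days | Unsplit table listed |
|---|---|---|
| Any adverse event | 3.1 | none |
| Maximum intensity | 3.4 | none |
| Drug-related | 3.5, 3.6 | none |
| Leading to discontinuation or withdrawal | 3.12 | none |
| Common non-serious | 3.7 (drug-related only) | 3.3 |
| Serious | 3.9 | 3.10 |

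The notes to Tables 3.1 and 3.9 already specify an unsplit version for Interim Analysis 1.

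**The case against.** The best defence is that nothing disappears. The SAP calls the later period follow-up and tabulates it with its own denominator. Figure 3.1 ranks events by overall number without a phase split, and Listings 15 and 17 cover all adverse events. The anticipated haematological effect is not cut at 28 days: SAP 7.2 runs worst-case laboratory summaries to the final follow-up visit and defines the nadir as the lowest post-baseline value. Protocol 10.3.1 makes the investigator's causality assessment the principal consideration, so a late event judged related still counts as drug-related. All of this stands, and it limits the point to the stated rationale and a gap in the tables.

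Two further defences stand in part. With about 15 participants on 300 mg, one participant exceeds 5%, so Table 3.3 may capture every non-serious term if its threshold applies within an arm; that is an assumption, since the shell is not in the SAP. For the same reason, it cannot be seen whether the by-phase shell carries an overall block. Neither supplies a specified whole-period count of participants with any event.

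A reader might go further in several ways that the documents do not support:
- **The SAP declares participants off drug.** The label is follow-up.
- **OSM is predicted to be largely neutralised after Day 99.** Protocol 5.5 predicts engagement only at trough during dosing; anything later is inference.
- **The arm comparison is biased in a known direction.** The same window applies to placebo, and no direction is shown.
- **The on-treatment phase should run to last dose + 126 days.** For a full course that is Day 71 + 126 = Day 197, the final visit, so no follow-up phase would remain. Only 2^(−126/19) = 1% to 2^(−126/25) = 3% of the drug is then left.
- **Exposure should be replaced by dosing duration.** For a full course that is 71 days against 99, which shortens a figure already said to end too early.

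**Conclusion.** The rationale is wrong as written. Twenty-eight days is 1.1 to 1.5 half-lives, with 36% to 46% of the drug remaining, and a typical fully dosed 300 mg participant enters the follow-up phase at about 1.1 to 2.2 times the 100 mg on-treatment peak. At the final analysis the listed tables give no whole-period participant count for any, drug-related, maximum-intensity or discontinuation-related adverse events.

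The concentrations assume linear kinetics, complete dosing and typical parameters. Someone who stopped after one or two 300 mg doses may already be at or below the 100 mg peak by the cut. If between-participant variation in CL/F and V/F were 20% to 40% (assumed; not in the documents), about 94% to 78% of 300 mg participants would exceed the typical 100 mg peak on that day. With a 19-day half-life and instant absorption the margin is only 8% and lasts about two days.

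The effect is on where late events are shown and how exposure is described. It does not support a reading that safety data are dropped.

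**What to change.** At the final analysis, add unsplit versions of Tables 3.1, 3.4, 3.5, 3.9 and 3.12, covering first dose to final follow-up (Day 197), with the Safety population as denominator. Make these the main adverse event displays and keep the 28-day split as supportive. Table 3.10 already covers serious events unsplit, so the added Table 3.9 is for a consistent format.

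In SAP 16.6.2, delete the reference to the half-life and state that 28 days is a reporting convention and not the end of drug exposure.

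The cost is SAP wording and a few extra tables from data already collected to Day 197. The downside is that unrelated late events are also counted, in both arms.

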16.6.3. Efficacy

Efficacy

CRISS Composite response index in dcSSc

CRISS is calculated in a two-step process (formula and text from Khanna, (2016)) and detailed in the section below.

There are two post-baseline assessments of CRISS. Each will use the initial baseline so that, for example, if a participant has a scleroderma renal crisis in the first CRISS period between baseline and week 12, they will receive a value of 0 for both the first CRISS period (week 12) and the second CRISS period (week 28) except for item (b). For item (b) participants will be classified based on their FVC at the current visit FVC regardless of their classification at previous assessments.

Step 1:

Participants who develop new or worsening cardiopulmonary and/or renal involvement due to systemic sclerosis are considered as not improved (irrespective of improvement in other core items) and assigned a probability of improving equal to 0.0. Specifically, if a subject develops any of the following:

- a) New scleroderma renal crisis^[1]
- b) Decline in FVC % predicted >= 15% (relative to baseline), HRCT to confirm ILD (if previous HRCT of chest did not show ILD) and FVC < 80% of predicted^{[2][3]}
- c) New onset of left ventricular failure (defined as left ventricular ejection fraction <= 45%) requiring treatment ^[1]^[2]
- d) New onset of PAH on right-sided heart catheterization ^[1] requiring treatment ^[1]^[2]

Notes:

1: Treating physician's judgement, is recorded directly in eCRF, details in SRM.

2: Attributable to systemic sclerosis

3: The three components of item b (FVC % predicted decline, absolute level of FVC % predicted and HRCT to confirm ILD) are recorded in the eCRF and will be derived by programming. Note that a historic diagnosis of ILD will be recorded in a different variable to one made during the study.

Items a) c) and d) are captured as part of the eCRF. Item b) the % predicted FVC criteria (>=15% declined from baseline and <80% at relevant visit) will be derived programmatically. HRCT is captured as part of the eCRF and is requested as required and at the discretion of the investigator.

- If the participant has a HRCT confirming ILD at or prior to the visit (including day 1 and screening period or historical diagnosis) they will be considered to have confirmed ILD. Then the % predicted FVC results would be used to assess if they meet part b) of step 1.

o CC o wł	Cl - This section contained Clinical Outcome Asse nich are protected by third party copyright laws ar	essment data collection questionnaires or indices, ad therefore have been excluded.
0		
0		
0		
0		
HAQ-DI		
There are 8 sec There are 2 or 3	ctions: dressing and grooming, arising, eatir 3 questions for each section. Scoring within	eg, walking, hygiene, reach, grip, and activities. each section is from 0 (PCI and activities) to 3
(CCI). I one question is	For each section the score given to that sec scored 1 and another 2, then the score for	tion is the worst score within the section, i.e. if that section is 2.

In addition, if an aide or devise is used or if help is required from another individual, then the minimum score for that section is 2. If the section score is already 2 or more then no modification is made. When there are

201247

no aids or devices or help indicated for a category, t	the category's score is not modified. Where the aid or
device for each section is:	

HAQ-DI Category	Companion AIDS OR DEVICES item
DRESSING &	Devices used for dressing (button hook, zipper pull, long handled shoe horn
GROOMING	etc.)
ARISING	Special or built up chair
EATING	Built up or special utensils
WALKING	Cane, walker, crutches, wheelchair
HYGIENE	Raised toilet seat, bathtub seat, bathtub bar, long handled appliances in
	bathroom
REACH	Long handled appliances for reach
GRIP	Jar opener (for jars previously opened).

If a response to a component question within a section is left blank, then the score for that section is determined by the remaining completed question(s) within the section.

The HAQ-DI is calculated from the taking the 8 scores of the 8 sections are summed and divided by 8. If one section is not completed by a participant, then the summed score would be divided by 7. At least 6 sections must be non-missing for the HAQ-DI to be calculated, else the HAQ-DI is set to missing.

VAS scales

Efficacv

VAS scales will be converted to a 0-3 scale before contributing to the SHAQ. The scaled VAS score will be calculated as: Scaled score = score*0.03. Scaled VAS scores will be presented in outputs.

Lab & Home FVC

Where multiple assessments are taken, the largest of the non-missing values will be used in the analysis.

